### **Method of Assigning Subjects to a Treatment**

All subjects who have signed the study ICF and meet all inclusion and no exclusion criteria will be randomized in a 1:1 into one of the two study arms (1) Aspirin 81 mg or 100 mg or (2) DOAC recommended dose. For study purposes, subjects are considered enrolled in the study once they have signed the consent form and are randomized and stratified by individual sites.

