**Safety Assessments**

**STROKE VT**

**Non-CABG Surgery Related Bleeding Events Criteria**

TIMI Major Bleeding Events
 
Any Symptomatic Intracranial Hemorrhage, or clinically overt signs of hemorrhage (including imaging) associated with a drop in hemoglobin of >5 g/dL (or when the hemoglobin concentration is not available, an absolute drop in hematocrit of >15% or Fatal Bleeding (bleeding that directly results in death within 7 days post procedure)

TIMI Minor Bleeding Events
 
Any clinically overt sign of hemorrhage (including imaging) that is associated with a fall in hemoglobin concentration of 3 to < 5 g/dL (or, when hemoglobin concentration is not available, an absolute drop in hematocrit of 9 to < 15%)

TIMI Bleeding Events Requiring Medical Attention
 
Any bleeding event that requires medical treatment, surgical treatment, or laboratory evaluation and does not meet criteria for a major or minor bleeding event, as defined above

Insignificant Bleeding Events (ie, TIMI Minimal Bleeding Event)
 
A reported blood loss or bleeding event episode not meeting any of the above criteria

Clinically Significant Bleeding Events
 
The composite endpoint of TIMI major bleeding event, TIMI minor bleeding event, or bleeding event requiring medical attention is considered clinically significant for the TIMI scale

Not a TIMI Bleeding Event

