### Secondary End Point Assessments

- A. Major bleeding events as defined above using TIMI criteria
- B. Minor Bleeding events as defined by the TIMI criteria

- C. Cardiovascular mortality
- D. All-Cause mortality
- E. Any other adverse events occurring during the study period

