### **DATA MONITORING COMMITTEE**

To meet the study's ethical responsibility to its subjects, an independent data safety monitoring Board (DSMB) will monitor results during the study. The board consists of 2 physicians and 1 statistician who have no formal involvement or conflict of interest with the subjects or the investigators. Records will be reviewed after the first 50 patients and then at the completion of the study.

If the major bleeding events in the DOAC group occur at >15% but <30% (absolute event rate) of those in the ASA group during any of the assessments, a recommendation will be made to consider modifying the study by the members of the DSMB. First consideration to modify is to decrease the dose of the drug to 2.5mg PO twice daily. If the major bleeding events in the DOAC group occur at >30% (absolute event rate) of those in the ASA group during any of the assessments, a recommendation will be made to stop the study by the members of the DSMB.

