### **STATISTICAL CONSIDERATIONS**

#### ***Study Management and Sample Size Justification***

This is a pilot study and 52 total patients will be enrolled in the study. We expect to analyze a total of 50 patients and each arm will consist of 25 patients. The additional 2 allows for attrition. Since this is a pilot study, the number needed to treat to achieve a pre-specified statistical significance cannot be calculated accurately. Exact sample size could not be given due to lack of pre-existing data on this subject. We hypothesize a 30% difference in outcomes can be seen with a total sample size of 50 patients.

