#### **Data Collection Center**

The Kansas City Heart Rhythm Research Foundation will be the coordinating site for the study. A project manager (PM) with the help of the PI will create the study worksheets and create the CRFs. The sites will complete the paper CRF and submit via secure email to the project manager. The PM will assist the Database Manager (DM) with updating the access database and providing computer support for outside centers. All data will be submitted via secure email including de-identified patient data that is to be used as source.

Participant's data will be de-identified and a code will be assigned. The code will consist of Site Number, Patient Number and Patient Initials. The coordinator at that site will have access to the code; the linking list will be destroyed at the completion of the project.

**Statistical analysis:** Patients will be randomized in a stratified manner to control arm versus treatment arm. We will analyze the differences in secondary endpoints between the two groups for major, minor bleeding and cardiovascular mortality up to 30 days post ablation. Categorical variables will be reported as counts and percentages and continuous variables will be expressed as mean  $\pm$  SD. Continuous variables will be compared using t-test for normally distributed data or Mann Whitney U test for non-normally distributed data as deemed appropriate. Categorical events will be compared using chi-square test for parametric data.

Univariate and multi-variate analysis will be performed to identify the predictors of systemic thromboembolic events and mortality. This is a pilot study to study the feasibility and safety of the study. A larger study will be done in the future if there is a positive signal.

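### The DSMB major-bleeding triggers do not say whether the percentage is an excess over aspirin or the DOAC arm's own rate, so one table can call for two different actions

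*Combined protocol and SAP*

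**What the plan says.** The combined protocol and SAP sets two triggers under Data Monitoring Committee. The lower one reads "If the major bleeding events in the DOAC group occur at >15% but <30% (absolute event rate) of those in the ASA group", and it leads to a recommendation to consider modifying the study, with a dose reduction to 2.5 mg twice daily as the first option. The upper one reads "If the major bleeding events in the DOAC group occur at >30% (absolute event rate) of those in the ASA group", and it leads to a recommendation to stop. On timing, the section says "Records will be reviewed after the first 50 patients and then at the completion of the study".

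Under Study Management and Sample Size Justification the plan says "We expect to analyze a total of 50 patients and each arm will consist of 25 patients", from 52 enrolled. Patients are "randomized and stratified by individual sites" in a 1:1 ratio. The counted event is set under Secondary End Point Assessments ("Major bleeding events as defined above using TIMI criteria"), and the criteria table under Safety Assessments gives the definition. The statistical analysis paragraph states the purpose: "This is a pilot study to study the feasibility and safety of the study".

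**The concern.** Each trigger carries two descriptions that do not fit together. The parenthesis points to an absolute rate, while the words after it make the figure a percentage of what happens on ASA. There is no formula, and neither sentence speaks of a difference or an excess. The bleeding definitions, the endpoint lists and the statistical analysis paragraph do not define the quantity either.

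A board applying the rule therefore has to choose a scale, and may have to do so with both arms' counts already in front of it. In a pilot that names safety as part of its purpose, a bleeding rule should give one answer from one table. Whether a trigger was crossed is also something readers will use when a larger trial is considered.

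**Working it through.** **Inputs from the documents.** Modify above 15% and below 30%; stop above 30% (Data Monitoring Committee). 25 patients per arm (Study Management and Sample Size Justification). The thresholds come with no derivation, so there is no figure of the plan's own to reproduce.

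**Notation.** *a* bleeds among *n* ASA patients; *d* bleeds among *m* DOAC patients.

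**Literal ratio**, (*d/m*)/(*a/n*). With 25 per arm, 2 against 2 gives 100% and stops the trial. ASA 2, DOAC 1 gives 50% and also stops it, although DOAC bleeds less. With no ASA bleeds the ratio is undefined. This reading is clearly unintended and is set aside.

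**Two absolute readings remain.**
- A: *d/m* − *a/n*, the excess over ASA.
- B: *d/m*, the DOAC arm's own rate.

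**Same table, both readings.** Site-stratified 1:1 allocation does not guarantee exactly equal arms, so 23/27 and 27/23 are included as assumed splits.

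| Bleeds (ASA, DOAC) | Arm sizes (ASA/DOAC) | A | B |
|---|---|---|---|
| 2, 5 | 25/25 | 20.0 − 8.0 = 12.0 points: no action | 20.0%: modify |
| 2, 5 | 23/27 | 18.5 − 8.7 = 9.8 points: no action | 18.5%: modify |
| 2, 5 | 27/23 | 21.7 − 7.4 = 14.3 points: no action | 21.7%: modify |
| 1, 8 | 25/25 | 32.0 − 4.0 = 28.0 points: modify | 32.0%: stop |
| 1, 8 | 23/27 | 25.3 points: modify | 29.6%: modify |
| 1, 8 | 27/23 | 31.1 points: stop | 34.8%: stop |

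At 25 per arm, B acts at 4 (modify) and 8 (stop) DOAC bleeds whatever the ASA count. A needs one more DOAC bleed for each ASA bleed: 5 and 9 with one ASA bleed, 6 and 10 with two. The readings agree when ASA has none.

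**How often the actions differ.** The documents give no major-bleeding rate, so every true rate below is an assumption. For independent binomial counts with 25 per arm, the probability of each pair (*a*, *d*) was summed over all pairs where A and B lead to different actions.

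| Assumed true rates, ASA / DOAC | Share of trials with different actions |
|---|---|
| 2% / 2% | 0.05% |
| 2% / 4% | 0.6% |
| 4% / 4% | 0.9% |
| 4% / 8% | 6.7% |
| 8% / 8% | 10% |
| *Stress cases:* 4% / 12% | 15% |
| 8% / 12% | 24% |
| 4% / 15% | 20% |
| 8% / 15% | 33% |
| 4% / 20% | 23% |
| 8% / 20% | 43% |
| 4% / 30% | 23% |
| 8% / 30% | 45% |

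In the first five rows the chance of a stop is at most 0.05% on either reading, so the difference there is almost entirely no action against modify. At 4% / 8%, for example, A modifies in 6.8% of trials and B in 13.5%. With unequal arms at 4% / 8%, the share that differs is 2.9% (23 ASA, 27 DOAC) or 5.8% (27 ASA, 23 DOAC).

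**The case against.** The strongest reply is that the intent is plain. Both sentences name the ASA group as comparator, and B has to ignore those words. A gives effect to both descriptions, and the statistical analysis paragraph likewise plans between-group comparisons of bleeding. This stands as far as likelihood goes: A is the better guess. But reaching A means departing from the literal wording, and the text does not say in which direction to depart.

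The second reply is that little turns on it. The board only recommends, and its members can weigh both arms' rates. The first review comes after 50 of 52 patients, so at most about two further enrolments could be affected, plus anyone still in the 30-day treatment period. The event is strict ("Any Symptomatic Intracranial Hemorrhage, or clinically overt signs of hemorrhage (including imaging) associated with a drop in hemoglobin of" more than 5 g/dL or its haematocrit equivalent, or fatal bleeding), so DOAC rates of 12% to 30% are stress cases. All of this stands, and it is why the point is minor. It does not give the rule a single meaning, and the stress cases are where a bleeding guard is needed.

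The third reply is that choosing A takes a decision from the sponsor, and that A is less protective because it acts later whenever ASA patients bleed. That is a real though small cost of A. If the sponsor meant B, it should say so; what matters is that one scale is written down.

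**Conclusion.** The concern holds, as a minor one. As worded, the triggers combine two scales. Taken literally they would stop the trial at equal bleeding, and the two sensible readings give different actions on tables such as 2 ASA and 5 DOAC bleeds in 25 per arm. That split does not depend on exactly equal arms, since it persists at 23/27 and 27/23. The practical size rests wholly on assumed bleeding rates: different actions in under 1% of trials at 2% to 4% per arm, 7% to 10% at 4%/8% and 8%/8%, and 15% to 45% in the stress cases. The late first review and the board's advisory role limit the effect further.

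**What to change.** In both trigger sentences of the Data Monitoring Committee section, replace the parenthesis and the reference to the ASA group with one scale: the DOAC major-bleeding rate minus the ASA major-bleeding rate, in percentage points, exceeds 15 (consider modifying) or exceeds 30 (stop). This gives effect to both of the present descriptions, and it still works with no ASA bleeds.

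Keep the percentages as the rule. Counts of 4 and 8 excess DOAC bleeds may be added only as an illustration for equal arms of 25 or 26. With no ASA bleeds, 27 DOAC patients would need 5 and 9, and 23 would need 4 and 7. The levels themselves remain for the sponsor and the DSMB to choose.

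The cost is two sentences, with no added patients, visits or procedures.

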### **STATISTICAL CONSIDERATIONS**

#### ***Study Management and Sample Size Justification***

This is a pilot study and 52 total patients will be enrolled in the study. We expect to analyze a total of 50 patients and each arm will consist of 25 patients. The additional 2 allows for attrition. Since this is a pilot study, the number needed to treat to achieve a pre-specified statistical significance cannot be calculated accurately. Exact sample size could not be given due to lack of pre-existing data on this subject. We hypothesize a 30% difference in outcomes can be seen with a total sample size of 50 patients.

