### **Overall Risk/Benefit Assessment**

Atrial fibrillation (AF) is associated with 5 times increased risk of cerebrovascular events compared to patients in Sinus rhythm [2]. Even in patients undergoing Radiofrequency Ablation (RFA) for atrial fibrillation, the incidence of symptomatic cerebrovascular events (CVE) was 2.3% and 41% of those are from transient ischemic attacks and 25% are from ischemic CVEs, despite being on anticoagulation. The incidence of asymptomatic CVEs rises to 14% after the ablation for AF, detected by Flair enhancement MRI. Multiple trials have shown that the asymptomatic CVEs and/or micro infarcts can increase the odds of having dementia. The incidence of stroke immediately after ablation for left ventricular arrhythmias has ranged from 0 to 2.7% to 7.5% depending on the case series, but there aren't many studies to quantify this problem clearly. Interestingly, the amount of tissue ablated in the ventricles is not any smaller than what is done in the left atrium. Even though the stunning phenomenon that is seen with the left atrial appendage may not be relevant to the ventricular tachycardia ablation, the extensive endothelial denudation and subclinical thrombus formation at the sites of ablation is clearly under appreciated. No active strategies to prevent post ablation systemic thromboembolization are available in patients undergoing left ventricular arrhythmia ablation especially on the left side. Similar to AF, the projected incidence of asymptomatic CVEs may be much higher than the incidence of symptomatic CVEs given the multiple reasons like heat generated from the

ablation, possibility of necrosis of myocardium from ablation and manipulation of the left side of the heart, but currently there are no studies that have focused on the incidence of asymptomatic CVEs. It has been therefore recommended to perform cardioversion or ablation only at therapeutic levels of anticoagulation to decrease the risk of thromboembolism and stroke. So far, there are no trials evaluating the efficacy of unfractionated heparin or newer direct thrombin or factor Xa inhibitors in preventing or reducing symptomatic and also asymptomatic CVEs post-left ventricular arrhythmia ablation. Given the high incidence of symptomatic CVEs and possibility of higher incidence of asymptomatic CVEs which has many prognostic implications, this issue warrants further studies.

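### The claim that 50 patients can show a 30% difference has no endpoint, scale, control rate, alpha or power behind it, and the event rates the protocol cites do not support it

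*Combined protocol and SAP*

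**What the plan says.** Under Study Management and Sample Size Justification the protocol describes a pilot that enrols 52 patients, 2 of them to cover attrition: "We expect to analyze a total of 50 patients and each arm will consist of 25 patients". It explains that "Exact sample size could not be given due to lack of pre-existing data on this subject". It then gives the only numerical link between that size and what the trial can show: "We hypothesize a 30% difference in outcomes can be seen with a total sample size of 50 patients".

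No alpha, sidedness, power or design event rate appears anywhere in the document. The only event rates are background figures under Overall Risk/Benefit Assessment:

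- After atrial fibrillation (AF) ablation, "the incidence of symptomatic cerebrovascular events (CVE) was 2.3" per cent.
- For MRI-detected lesions, "The incidence of asymptomatic CVEs rises to 14% after the ablation for AF".
- For the procedure under study, "The incidence of stroke immediately after ablation for left ventricular arrhythmias has ranged from 0 to 2.7% to 7.5" per cent, depending on the case series.

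The same section says that asymptomatic events after left ventricular ablation "may be much higher than the incidence of symptomatic CVEs", but that "currently there are no studies that have focused on the incidence of asymptomatic CVEs".

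The primary endpoint (Primary Objectives; Primary End Point Assessment) combines stroke, TIA, asymptomatic MRI lesions and systemic embolism. The Statistical analysis paragraph plans a chi-square test for categorical events, without saying whether it is continuity-corrected. It describes the trial as a pilot of feasibility and safety that may lead to a larger study.

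**The concern.** A pilot does not need a power calculation, but a capability that it does state should be interpretable. This one is not. An absolute 30-point fall and a relative 30% fall are very different effects, and at the rates the protocol cites one is impossible and the other practically undetectable with 25 per arm.

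What is at stake is how a null result is read. Because 30% is the only stated capability, a reader may take a non-significant comparison as evidence against an effect of that size. If 30% is relative, the pilot would often not even point the right way when the effect is real, whatever test or decision rule is used.

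**Working it through.** **Inputs from the document.** 25 analysed per arm; 1:1 allocation; chi-square test; cited rates of 2.3%, 2.7%, 7.5% and 14%.

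**Assumptions, because the document is silent.** Two-sided alpha of 0.05, with one-sided 0.05 as a variant; 80% power as the benchmark; aspirin rates of 30% and above for the unknown true rate. Two sums stand in for a composite: 14% + 2.3% = 16.3%, and 14% + 7.5% = 21.5%. The second adds an AF lesion rate to a left ventricular stroke rate and is an assumed upper case.

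**1. Can the plan's figure be reproduced?** The head count is consistent: 25 + 25 = 50 and 50 + 2 = 52. The 30% cannot be derived, because its inputs are missing. Working backwards with the usual formula,

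n per arm = [1.96·√(2·p̄(1−p̄)) + 0.842·√(p₁(1−p₁) + p₂(1−p₂))]² / (p₁−p₂)²

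an absolute fall from 33% to 3% (p̄ = 0.18) gives (1.065 + 0.421)² / 0.09 = 24.5, so 25 per arm. A 30-point fall from about one third therefore fits 50 patients, but the protocol states no such rate.

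**2. Exact power with 25 per arm.** With a aspirin events, b DOAC events and s = a + b, the uncorrected statistic is X² = 50(a−b)² / [s(50−s)]. Power is the total binomial probability of all 26 × 26 outcomes with X² > 3.84.

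Relative 30% reduction:

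| Aspirin rate | DOAC rate | Power, two-sided | Power, one-sided |
|---|---|---|---|
| 2.3% | 1.6% | 0.2% | 1.3% |
| 2.7% | 1.9% | 0.3% | 1.8% |
| 7.5% | 5.25% | 3.9% | 8.8% |
| 14% | 9.8% | 7.6% | 12.6% |
| 16.3% | 11.4% | 8.3% | 13.3% |
| 21.5% | 15.05% | 9.6% | 15.0% |
| 30% | 21% | 11.8% | 17.9% |
| 50% | 35% | 21.6% | 30.9% |

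At 14%, the expected counts are 25 × 0.14 = 3.5 against 25 × 0.098 = 2.45 events. Two-sided power reaches 80% only at an aspirin rate just above 95%.

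Absolute 30-point reduction (impossible below an aspirin rate of 30%):

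| Aspirin to DOAC | Power, two-sided |
|---|---|
| 30% to 0% | 97% |
| 35% to 5% | 83% |
| 36% to 6% | 80% |
| 40% to 10% | 73% |
| 50% to 20% | 64% |
| 65% to 35% | 62% |
| 94% to 64% | 80% |

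Aspirin rates at which this reduction has at least 80% power, by test:

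- Uncorrected, two-sided: 30.0–36.2%, or 93.8% and above.
- Uncorrected, one-sided 0.05: 30.0–41.7%, or 88.3% and above.
- Continuity-corrected, two-sided: 30.0–30.1%, or 99.9% and above.
- Fisher's exact, two-sided: 30.0–30.6%, or 99.4% and above.

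**3. Direction of the observed result under a true relative 30% reduction.** Probability that the DOAC arm shows at least as many events as the aspirin arm:

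| Aspirin rate | DOAC higher | Tie | Total |
|---|---|---|---|
| 14% | 24.6% | 15.9% | 40.5% |
| 21.5% | 21.7% | 12.3% | 34.1% |
| 30% | 18.4% | 9.9% | 28.3% |
| 50% | 11.0% | 6.4% | 17.3% |

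(Components may not add exactly because of rounding.)

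**4. Precision the design does deliver.** With the same rate p in both arms, the normal-approximation half-width of the 95% interval for the risk difference is 1.96·√(2p(1−p)/25). At 14% this is 1.96·√(0.2408/25) = 0.192. The Newcombe half-width is averaged over all outcomes.

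| Event rate | Normal | Newcombe |
|---|---|---|
| 2.3% | not used, too few events | 15 points |
| 7.5% | not used, too few events | 17 points |
| 14% | 19 points | 20 points |
| 21.5% | 23 points | 22 points |
| 30% | 25 points | 24 points |
| 50% | 28 points | 25 points |

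**The case against.** The protocol is open about its limits. It calls itself a pilot, says a significance-based number cannot be calculated accurately, introduces the 30% as a hypothesis and frames its primary objective as estimation. No stopping or progression rule uses the figure. The head count is right, so this is a missing-assumptions point rather than a wrong sum.

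Nor were the cited rates offered as design assumptions: two come from AF ablation, and the left ventricular figure is stroke alone. If MRI lesions are common in this population and the aspirin rate is near one third, a 30-point absolute fall would be well within reach of 50 patients. The direction argument applies only if 30% is relative, and part of those percentages is ties.

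Most of this stands. It is why the sentence cannot be called false, and why no change of sample size follows. It does not rescue the sentence, because the disclaimers are followed directly by a statement of what 50 patients can show, without the inputs needed to interpret it. An unstudied event rate is a reason to state the assumed rate, not to omit it. Ties do not help either, since a tied result also fails to show the right direction.

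**Conclusion.** The concern holds and should be fixed. The 30% statement cannot be reproduced, and no rate in the document supports it on either scale: an absolute 30-point fall is impossible from those rates, and a relative 30% fall has less than 10% two-sided power up to the assumed upper case of 21.5%. The sentence could be true only under an unstated aspirin rate, roughly 30–36% for an absolute fall with the uncorrected two-sided test. The size of that window rests on an assumed alpha of 0.05 and the 80% benchmark. One-sided testing widens it to about 42%, while a continuity correction or Fisher's test shrinks it to about 30%. Because the true composite rate in this population is unknown, the claim is unsupported, not disproved. The design and the number of patients are not in question.

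**What to change.** Keep 52 patients and replace the sentence with the precision the design gives, for example:

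> With 25 patients per arm, the 95% confidence interval for the risk difference has a half-width of about 19–28 percentage points for event rates of 14–50% (normal approximation, same rate in both arms; approximate at the low end). The event rate in this population is unknown. The pilot is not powered to test efficacy, and a non-significant result will not be read as absence of effect.

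To cover the low cited rates as well, use the Newcombe form: about 15–17 points at 2.3–7.5% and 20–25 points at 14–50%. If the sponsor prefers to keep a detectable difference, state its endpoint, scale, assumed aspirin-arm rate, alpha, sidedness, test and power. Defining what result would justify the larger study is a separate, secondary point.

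The cost is wording only: no extra patients and no change to conduct. The downside is a less favourable stated capability.
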